2.1. Multiplicity Adjustment

This is a proof of concept study. No adjustments will be made to adjust the performed efficacy analysis for multiplicity.

3. Analysis Sets

The following analysis data sets are defined to estimate the estimands defined in the protocol and to address safety.

Analysis Data Sets	Description
Full Analysis Set (FAS) for the primary estimand and for the secondary estimand for the secondary objective	
• All participants randomly assigned to study intervention and who take at least 1 dose of study intervention. Participants will be included in the analyses according to the planned intervention• For participants who discontinue study intervention and/or receive rescue therapy, post-discontinuation or post-rescue observations will not be included.
Safety analysis set to be used for safety assessments	
• All participants who are exposed to study intervention. Participants will be included in the analyses according to the intervention they actually received.• All observed data will be included in the analysis set.
Pharmacokinetic(PK) analysis set to be used for PK assessments	
• All participants randomly assigned to study intervention and who take at least 1 dose of study intervention and have PK data available.• All observed data until discontinuation of intervention will be included in the analysis set.

4. Statistical Analyses

4.1. General Considerations

The independent variable, previous RA therapy population, is defined as only csDMARD experienced or bDMARD/tsDMARD experienced participants. Unless otherwise indicated in the statistical analysis plan (SAP), the analyses will be conducted as follows:

Analysis for	Description
Primary and secondary endpoint analyses comparing LY3462817 to placebo	Tested at a 2-sided level of 0.05 for frequentist analyses
Adjustments for multiplicity	None to be performed
Baseline	Defined as the last available value before the first dose of study intervention for both efficacy and safety analyses. In most cases, this value will be what is recorded at the randomization visit (Visit 2).
Change from baseline	Will be calculated as the visit value of interest minus the baseline value.
Efficacy and patient-reported outcome (PRO) analysis	Analysis models may contain the independent variables such as treatment group, baseline disease activity, and previous RA therapy population. Endpoint analyses will use the FAS unless otherwise specified.
Dichotomous responder endpoints	Missing data will be imputed using the nonresponder imputation (NRI) method. Will be analyzed using a logistic regression model with treatment group, baseline disease activity, and previous RA therapy population as model covariates.
NRI analysis	Participants will be considered nonresponders if: 
 • they do not meet all the clinical response criteria • they are noncompliant with concomitant medication rules

	
 • they permanently discontinue study intervention at any time before the end of the treatment period for any reason, or • they are randomized and do not have at least 1 postbaseline observation.
Continuous efficacy endpoints	
Mixed-effects model for repeated measures (MMRM) will be used.
 
The MMRM model will include treatment, strata (previous RA therapy population), baseline value, visit, treatment-by-visit interaction in the model as fixed factors, and patient as a random factor.
 
An unstructured covariance matrix will be used to model the within-subject errors. If this analysis fails to converge, other structures will be tested (in this order: Toeplitz, Autoregressive with heterogeneity, and compound symmetry.).
 
The Kenward-Roger approximation will be used to estimate denominator degrees of freedom. Significance tests will be based on least squares means and Type III tests.

Participant Disposition	
A detailed description of participant disposition will be provided, including a summary of the number and percentage of participants entered into the study and randomized, and number and percentage of participants who complete the study or discontinue, both overall and by reason for discontinuation. A summary of important protocol deviations will be provided.

Participant Characteristics	
Demographic data are collected and responded to demonstrate that the study population represents the target patient population. A summary of baseline participant characteristics, historical diagnoses, preexisting conditions, and prior therapies will be reported by treatment group using descriptive statistics. Other participant characteristics will be summarized by treatment group as deemed appropriate.

Concomitant Therapy	
Previous and concomitant medications will be summarized by treatment group and will be presented by Anatomical Therapeutic Chemical drug classes using the latest version of the WHO drug dictionary.

Treatment Compliance	No analyses are planned to assess treatment compliance, given that participants will receive study intervention directly from the investigator or designee at the study site, under medical supervision.
----------------------	--

Summary statistics for continuous measures will include sample size, mean, standard deviation, median, minimum, and maximum.

For categorical data, summary statistics will include sample size, frequency, and percentages. Percentages will be rounded to one decimal place. Unless otherwise specified, Fisher's exact test will be used for making treatment comparisons.

All statistical tests of treatment effects will be performed at two-sided significance levels of 0.05 and 0.10, respectively, unless otherwise specified. All p-values will be presented to three decimal places.

The Treatment Period is defined as the combination of Period 1 with double-blind treatment and Period 2.

The baseline period is defined as Visit 1 through pre-dose Visit 2. The Double-blind Treatment Period starts after the first injection of study treatment at Visit 2 (Week 0) and ends on the date of Visit 6 (Week 12) or the early discontinuation visit. The Period 2 starts after the date of Visit 6 (Week 12) or the early discontinuation visit and lasts up to 24 weeks following the last injection of study treatment. Additional follow-up beyond 24 weeks may be deemed necessary and, if so, any data collected will be considered as part of Period 2.

Unless otherwise specified, baseline for the Treatment Period is defined as the last non-missing assessment on or prior to the date of the first injection of study treatment, scheduled to be given at the end of Visit 2. Any assessment collected after the first injection through the date of the Week 12 or early discontinuation visit is defined as post-baseline for the Treatment Period.

Data collected at early discontinuation visits will be mapped to the next planned visit number for that patient. For by-visit summaries, only visits in which a measure was scheduled to be collected will be summarized.

Summaries of safety data collected during Period 2 will be presented separately. Unless otherwise specified, follow-up baseline is defined as the last non-missing assessment on or prior to the date of Week 12 or the date of the early discontinuation visit.

Change from baseline will be calculated as the post-baseline value minus the baseline value. Percent change from baseline is defined as $(100 \times (\text{post-baseline} - \text{baseline}) / \text{baseline})$. If all baseline values are missing for a particular variable, the change from baseline and percent change from baseline will not be calculated.

The statistical analyses of efficacy, health outcomes, and safety measures will be performed using SAS Version 9.4 or higher. Lilly will be responsible for conducting analyses.

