4.1. Overall Design

This is a Phase 2, proof-of-concept, placebo-controlled, double-blind, randomized study in adult participants with moderately to severely active RA who have had an inadequate response to csDMARDs, or to bDMARDs/tsDMARDs. Participants will be administered LY3462817 or placebo IV Q4W.

Screening Period (Visit 1, Days -42 to -1)

Participants will sign the informed consent document(s) at Visit 1, prior to completion of any procedures. Participants will be evaluated for study eligibility \leq 42 days prior to the baseline visit (Visit 2).

Period 1: Double-blind Treatment (Visits 2 to 6; 12 weeks)

At the baseline visit (Visit 2), participants who fulfill the eligibility criteria will be randomized to receive LY3462817 700 mg, LY3462817 300 mg, or placebo in an allocation ratio of 2:1:1.

The double-blind treatment period will establish the clinical efficacy and safety of LY3462817. The study will be evaluated for the primary objective at the end of the double-blind treatment period.

Period 2 (Visits 6 to 10; 12 weeks)

Data from a Study KDAC interim analysis that includes Week 12 data from participants in the KDAC 700-mg cohort, must be reviewed prior to a participant proceeding to Period 2 in Study KDAD.

At Week 14, participants will be evaluated for clinical benefit.

Participants assigned to LY3462817 at baseline, and achieving low disease activity (CDAI \leq 10) at Week 14 will continue to receive LY3462817 at the randomized dose through Week 24 to assess safety and tolerability and evaluate efficacy.

All other participants at Week 14, regardless of baseline treatment assignment, will stop study drug infusions and should receive standard of care treatment at the investigator's discretion.

Posttreatment Safety Follow-up Period (Visits V801 and 802; 12 weeks)

Following Period 2, participants will be followed posttreatment for 12 weeks to assess safety, study drug exposure, and clinical disease activity measures. Participants who discontinue the study intervention per Section 7 will have their last visit at 12 weeks from the last administration of the study intervention.

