6.5.2. Prohibited Concomitant Therapy

Live vaccinations are not allowed up to 3 months prior to screening or at any time during the study. Live herpes zoster vaccination is not permitted within 30 days of planned randomization or at any time during the study.

Nonlive seasonal vaccinations and/or emergency vaccination, such as rabies or tetanus vaccinations, are allowed.

6.5.3. Standard of Care Therapy after Week 14

All placebo patients should begin SOC therapy at Week 14 at the investigator's discretion.

Participants randomized to LY3462817 at baseline and not achieving low disease activity (CDAI ≤ 10) at Week 14 will no longer receive study drug infusions and should receive SOC therapy at the investigator's discretion.

Participants who achieve low disease activity at Week 14, and maintain treatment with LY3462817 during Period 2, can be switched to SOC prior to Week 24 if the participant stops receiving clinical benefit. Name(s) and dosage regimen(s) must be recorded for the SOC therapy. Standard of care medications will not be supplied by the sponsor.

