4.4.1.2. Main analytical approach

4.4.1.2.1 ACR20

The frequency and percentage of patients achieving ACR20 response will be summarized by treatment arm at each post-baseline visit. A logistic regression model will be used to test the treatment difference of each LY dose versus placebo at each post-baseline visit with treatment group, baseline disease activity, and previous RA therapy population as model covariates. Baseline DAS28-CRP score will be used as the baseline variable. NRI as described in Section 4.1 will be used to impute missing data for ACR20 in patients who were Week 12 non-responders or who discontinued prior to Week 12.

The Kaplan-Meier estimator will be used to summarize time to ACR20 response over 12 weeks and a plot by treatment arm will be presented. Week 12 non-responders will be censored on the date of the Week 12 visit. All patients ongoing at Week 12 and who have not yet responded will be censored on the date of the Week 12 visit. A Cox proportional hazards model will be used to test the treatment comparison between each LY dose and placebo in time to ACR20 response over 12 weeks.

For participants who discontinue study intervention and/or receive rescue therapy, post-discontinuation or post-rescue observations will not be included.

Subjects with ACR20 response will also be listed.

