4.5.4 CDAI Remission and Low Disease Activity

Remission is defined as a CDAI score of ≤ 2.8 . Low disease activity is defined as a CDAI score of ≤ 10 .

The frequency and percentage of patients achieving remission and low disease activity will be summarized by treatment arm at each post-baseline visit. A logistic regression model will be used to test the treatment difference of each LY dose versus placebo at each post-baseline visit with treatment group, baseline value, and previous RA therapy population as model covariates. NRI as described in Section 4.1 will be used to impute missing data for CDAI remission and low disease activity in patients who were Week 12 non-responders or who discontinued prior to Week 12.

The analyses for CDAI remission and CDAI LDA will be repeated for all visits in period 2. NRI as described in Section 4.1 will be used to impute missing data for CDAI in patients who were Week 24 non-responders or who discontinued prior to Week 24.

For participants who discontinue study intervention and/or receive rescue therapy, post-discontinuation or post-rescue observations will not be included.

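### The non-responder rule in SAP 4.1 runs to the end of a treatment period defined as Periods 1 and 2, so the planned Week 14 stop makes placebo non-responders in the Period 2 tests and leaves the Week 12 rule ambiguous

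*SAP*

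**What the plan says.** **General rule.** The table in SAP 4.1 lists four routes to non-response. The third is that "they permanently discontinue study intervention at any time before the end of the treatment period for any reason". Protocol 9.4.1 has the same bullet. The table is introduced by "Unless otherwise indicated in the statistical analysis plan (SAP), the analyses will be conducted as follows".

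**Meaning of the period.** Later in SAP 4.1: "The Treatment Period is defined as the combination of Period 1 with double-blind treatment and Period 2". The same section also uses the term more narrowly: an assessment after the first dose and "through the date of the Week 12 or early discontinuation visit is defined as post-baseline for the Treatment Period".

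**Week 12 responder sections.** SAP 4.4.1.2.1 applies NRI as described in Section 4.1 to "impute missing data for ACR20 in patients who were Week 12 non-responders or who discontinued prior to Week 12", in an analysis run at each post-baseline visit. ACR50/70 follow ACR20. SAP 4.5.1 to 4.5.5 use the same Week 12 pattern.

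**Period 2 responder sections.** SAP 4.5.1 to 4.5.4 repeat the remission and low-disease-activity analyses at all Period 2 visits. The CDAI text uses NRI to "impute missing data for CDAI in patients who were Week 24 non-responders or who discontinued prior to Week 24". SAP 4.5.7 tests ACR20/50/70 for each LY3462817 dose against placebo at each Period 2 visit, with a cut at Week 23. Observations after discontinuation or rescue are excluded.

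**Who stops at Week 14.** Protocol 6.5.3: "All placebo patients should begin SOC therapy at Week 14". Protocol 4.1 says that everyone not continuing LY3462817, regardless of baseline assignment, "will stop study drug infusions and should receive standard of care treatment". Only participants assigned to LY3462817 with CDAI ≤10 at Week 14 continue. SAP 1.2 differs: it has all subjects receiving LY3462817 in Period 2.

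**The concern.** The rule applies to stopping for any reason, and no sentence exempts a stop that the protocol itself plans. Joined to the Period 1 plus Period 2 definition and the protocol's Week 14 rule, it makes the whole placebo arm non-responders, together with every LY3462817 participant not in low disease activity at Week 14. LY3462817 participants who continue keep whatever response they have. A contrast built this way comes from who was allowed to stay on study drug. It says nothing about the drug's effect on response.

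There is a second, separate fault. Responder status is analysed visit by visit, but the sections decide whose missing data are imputed by looking at status at Week 12 or Week 24. On that wording, a missing Week 8 value is set to non-response for someone who later fails at Week 12, with no matching instruction for someone who later responds. Handling at one visit then depends on a future outcome.

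At stake are the secondary ACR20/50/70 results and the exploratory remission and low-disease-activity results.

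**Working it through.** **1. The plan's own figure.** The only design figure is power above 80% for DAS28-CRP change at Week 12 (SAP 5, protocol 9.2): means -1.80 and -0.75, SD 1.25, 40 against 20 participants, two-sided 0.05.

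Noncentrality = 1.05 / (1.25 × √(1/20 + 1/40)) = 1.05 / 0.342 = 3.07. With 58 degrees of freedom the power is 85.5% (86.6% by the normal approximation). The stated figure is reproduced. It does not depend on NRI.

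**2. Number of placebo participants forced to non-response by the Week 14 stop** (planned arm size 20):

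| Analysis | Cut applied | Forced |
|---|---|---|
| Week 12 endpoints | Stopped before Week 12 (4.4.1.2.1, 4.5.1 to 4.5.5) | 0 of 20 |
| Week 12 endpoints | Literal 4.1 rule, end of Period 2 | 20 of 20 |
| Period 2 visits | Week 24 (4.5.1 to 4.5.4) or Week 23 (4.5.7), planned stop not exempted | 20 of 20 |

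The first two rows conflict, and both can be reached from the SAP read with the protocol. In the third row the endpoint-specific text gives no relief, because its cut lies after Week 14.

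**3. What a zero placebo count does to the test.** With 0/20 responders, the likelihood of a logistic model keeps rising as the placebo log-odds fall. The treatment coefficient therefore has no finite maximum-likelihood estimate, whatever the 700 mg count (provided it is not also zero).

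**4. Illustration of size, by Fisher's exact test, placebo fixed at 0/20.** For 8/40 on 700 mg there are 8 responders among 60. The probability that none is on placebo is C(52,20)/C(60,20) = 0.0301. Adding the equally or less likely tables in the other tail (0.0118 + 0.0012 + 0.00005) gives p = 0.043. With 7/40, p = 0.084. So 8 counted responders suffice.

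P(p<0.05) = P(X ≥ 8), X ~ Bin(40, c), where c is the share of the 700 mg arm still counted as responders after the same rule has been applied to that arm:

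| c (assumed) | P(p<0.05) |
|---|---|
| 10% | 4% |
| 15% | 24% |
| 20% | 56% |
| 25% | 82% |
| 30% | 94% |

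For comparison, with equal true rates of 20% to 40% in both arms and no forced failures, the same Fisher test rejects in about 3.5% of trials. The documents give no responder rates, so every value of c is an assumption.

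**The case against.** The strongest reply concerns Week 12, and much of it stands.

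- Section 4.1 yields to other SAP text, and each Week 12 responder section names discontinuation before Week 12.
- SAP 4.1 ends the Double-blind Treatment Period at Week 12, and the protocol places its composite responder strategy under estimands for that period.
- The primary lock comes when all participants have completed Period 1 or stopped treatment (protocol 9.5, SAP 4.8). Some will not have reached Week 24, so a rule needing Period 2 status could not be fully applied then.
- Protocol 7.1.2 describes permanent discontinuation as rare, which fits poorly with a planned switch of at least a quarter of the participants (20 of 80).
- The forced result needs the protocol's Week 14 rule. Under SAP 1.2 alone, placebo participants would not stop study drug.

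A reader might infer that placebo response at Week 12 will certainly be zero. These points show that the documents do not support that. They indicate intent, however, and do not repair the text: 4.4.1.2.1 calls the Section 4.1 rule, whose bullets classify participants whether or not a value is missing.

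A reader might also take 56% and 94% as false-positive rates when both arms have true response rates of 20% or 30%. They are not. The rule also removes LY3462817 responders who are not in low disease activity at Week 14, so the counted rate cannot exceed the true rate. The plan specifies logistic regression for these endpoints, not Fisher's test.

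On missing intermediate visits, Section 4.1 says generally that missing data are imputed by NRI. Leaving a later responder's Week 8 value missing is therefore one reading of the endpoint sections, not the only one.

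None of this rescues the Period 2 tests against placebo.

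**Conclusion.** Wrong as written, but below must-fix: only secondary and exploratory responder analyses are touched, and the primary MMRM does not use NRI.

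- **Period 2 responder tests:** unless the planned stop is exempted, all 20 placebo participants are non-responders by rule, as are all LY3462817 participants not in low disease activity. The tests are then uninterpretable as evidence of drug effect. This rests on the current protocol's Week 14 text, which SAP 1.2 contradicts.
- **Week 12 endpoints:** the rule is ambiguous. A Week 12 cut is the more likely intent, with no forced failures; a literal implementation gives 0/20.
- **Imputation conditioned on later status:** a separate drafting fault in 4.4.1.2.1 and the visit-by-visit analyses in 4.5.

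The Fisher figures show only how easily a forced 0/20 yields a nominally significant difference. They depend on assumed counted rates.

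**What to change.** 1. In SAP 4.1 and protocol 9.4.1, replace the discontinuation bullet with: non-responder at visit v if study intervention was permanently discontinued before visit v, or if the value at visit v is missing.
2. State that the protocol-planned stop at Week 14 is not a discontinuation for Period 1 endpoints.
3. Delete the condition on Week 12 or Week 24 non-responders from SAP 4.4.1.2.1 and 4.5.
4. Make the Period 2 responder summaries (4.5.1 to 4.5.4 and 4.5.7) descriptive, without a test against placebo. Step 1 alone is not enough, because a visit-based rule can still force placebo failures at Weeks 16 to 24.
5. Reconcile the Period 2 description in SAP 1.2 with the current protocol. The SAP states that it is based on the protocol dated 05AUG2020 and declares no changes to the planned analyses.

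The cost is wording in the SAP and one bullet in the protocol. Protocol 9.4.1 requires an amendment only where a principal feature changes; other changes can be described and justified in the SAP and study report. Sample size, data collection and the primary analysis are unchanged. The revision should be final before any unblinding, including the interim analysis.

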Administer study drug		X		X	X	X		X	X	X				During Weeks 16 - 24 administer study drug only if participant achieved low disease activity at Week 14.

Abbreviations: AESI = adverse event of special interest; anti-HBc = hepatitis B core antibody; BP = blood pressure; C-SSRS = Columbia-Suicide Severity Rating Scale; ECG = electrocardiogram; ED = early discontinuation visit; ET = early termination; ETV = early termination visit; HBcAb+ = hepatitis B core antibody positive; HBsAg = hepatitis B surface antigen; ICF = informed consent form; IgA = immunoglobulin A; IgG = immunoglobulin G; IgM = immunoglobulin M; MRI = magnetic resonance imaging; PD-1 = programmed cell death protein 1; PD-L1 = programmed cell death ligand 1; PPD = purified protein derivative; PR = pulse rate; RA = rheumatoid arthritis; T = temperature; TBNK = T cells, B cells, natural killer cells; V = visit; VAS = visual analog scale.

2. Introduction

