4.6.1. Extent of Exposure

Duration of Exposure to Study Treatment

Duration of exposure on treatment (defined as time since first injection in days) during the Double-blind Treatment Period will be summarized by treatment arm and provided as listing. Duration of exposure on treatment will be calculated as:

(Date of last study visit during the Double-blind Treatment Period – Date of first injection + 1).

For patients who discontinue from the treatment, the date of discontinuation prior to Period 2 will be used.

Descriptive statistics for duration of exposure and the frequency and percentage of patients falling into the following ranges will be summarized: 0, >0, ≥ 7 days, ≥ 14 days, ≥ 30 days, ≥ 60 days, ≥ 84 days. The frequency and percentage of patients with duration of exposure in the following categories will also be summarized: 0 days, <14 days, ≥ 14 to <30 days, ≥ 30 to <60 days, ≥ 60 to <84 days, ≥ 84 days.

Overall exposure for each treatment arm will also be summarized in total patient years. This will be calculated as follows:

Exposure in patient years = Sum of duration of exposure (for all patients in treatment arm) / 365.25.

The analyses in Double-blind Treatment Period will be repeated for all visits in period 2 for subjects who remain on LY3462817 300 mg or LY3462817 700 mg.

Total Dose of Study Treatment

Total dose of active study treatment per subject will be summarized by active treatment arm using descriptive statistics. The total dose (mg) will be calculated as:

Total Dose = Sum over all injections received of [dose of LY (mg) prescribed per injection]

A by-patient listing of exposure duration and total dose will be provided.

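### The SAP closes the double-blind period on the day of the fourth infusion (Visit 6), so no planned safety or exposure summary gives the full randomised comparison to Week 14

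*SAP*

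**What the plan says.** **SAP.** Under section 4.1 the Double-blind Treatment Period "ends on the date of Visit 6 (Week 12) or the early discontinuation visit", and "The Period 2 starts after the date of Visit 6 (Week 12) or the early discontinuation visit". The same section adds: "Summaries of safety data collected during Period 2 will be presented separately". It stops post-baseline assessments for the Treatment Period at the Week 12 (or early discontinuation) visit and takes the follow-up baseline at or before that visit. In section 4.6.1, double-blind exposure is counted to the last visit of that period, and for Period 2 the analysis "will be repeated for all visits in period 2 for subjects who remain on LY3462817 300 mg or LY3462817 700 mg".

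Section 4.1 also defines the Treatment Period as Period 1 plus Period 2. Section 4.6.2 counts treatment-emergent events from first dose to Visit 10 (Week 24), and section 4.6 gives safety summaries a placebo column.

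**Protocol.** In the Schedule of Activities (1.3), the row "Administer study drug" is marked at Visits 2, 4, 5 and 6 (Weeks 0, 4, 8 and 12) and then at Visits 8, 9 and 10. Its only condition is: "During Weeks 16 - 24 administer study drug only if participant achieved low disease activity at Week 14". Section 6.5.3 says: "All placebo patients should begin SOC therapy at Week 14". Sections 4.1 and 6.5.3 stop infusions at Week 14 for LY3462817 participants who have not reached low disease activity.

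**The concern.** The cut falls two weeks before the arms diverge. From first infusion to Visit 7, all three arms are on what they were randomised to. After Week 14, placebo participants and LY3462817 non-responders go to standard of care, and only LY3462817 responders continue. A summary to Week 12 stops on the fourth dosing day, and a summary to Week 24 mixes randomised time with time in groups selected by response. Neither is the full randomised comparison.

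Safety and tolerability against placebo is a secondary objective. Hypersensitivity, infusion site reactions and infections are events of special interest, and SAP 4.6.2.1 has its own category for delayed reactions. The protocol (2.2) gives a half-life of about 10 days, so Weeks 12 to 14 are on-drug time. The fourth infusion is the last one with a concurrent placebo group. What happens after its dosing day therefore belongs in a controlled summary, with a matching exposure denominator.

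**Working it through.** **1. Inputs.** Nominal visit days come from the Schedule of Activities: Visit 6 is day 84 and Visit 7 is day 98, each ±7 days. Infusions up to Week 12 fall on days 0, 28, 56 and 84, counted from first infusion. Arm sizes are 40 (700 mg), 20 (300 mg) and 20 (placebo), from Protocol 9.2. Full retention is assumed.

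**2. The plan's own figures.** The stated 12 weeks for Period 1 is 12 × 7 = 84 days, which matches Visit 6. The sample-size statement (700 mg against placebo, difference 1.05, SD 1.25, more than 80% power) also reproduces: a noncentral t with 58 df gives 85.5%. It does not depend on where the safety period closes.

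**3. Where the arms diverge.** Only the Weeks 16 to 24 infusions are conditional, so the Week 12 infusion is due in every arm. Stopping and standard of care begin at Week 14. The randomised window is therefore days 0 to 98, and the part outside the SAP's double-blind period is 98 − 84 = 14 days, or 14/98 = 14.3%.

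**4. Infusions and person-time.** Person-years = n × days / 365.25. The extra day in the SAP's duration formula cancels in the differences, which are taken before rounding.

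| | Close at Visit 6 (84 days) | Close at Visit 7 (98 days) | Difference |
|---|---|---|---|
| Infusions followed beyond the dosing day | 3 of 4 | 4 of 4 | 1 |
| 700 mg (n = 40), person-years | 9.20 | 10.73 | 1.53 |
| 300 mg (n = 20), person-years | 4.60 | 5.37 | 0.77 |
| Placebo (n = 20), person-years | 4.60 | 5.37 | 0.77 |
| All (n = 80), person-years | 18.40 | 21.46 | 3.07 |

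By dose count, the fourth infusion is 80 of 4 × 80 = 320, or 25%. With the ±7-day windows, the gap from Visit 6 to Visit 7 can be 0 days (91 to 91) up to 28 days (77 to 105).

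**5. Dilution.** In the nominal Weeks 12 to 24 block, the two randomised weeks are 14/84 = 16.7% of the time.

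**6. Exposure.** Placebo time after Visit 6 is in no duration summary, because the Period 2 repeat covers only those still on LY3462817. On the natural reading, LY3462817 participants stopped at Week 14 are also outside that repeat. The documents do not say how many will stop. If 60% to 85% of the 60 did (an assumption), that would be 36 to 51 people and 72 to 102 person-weeks of duration up to Week 14.

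**7. Where events land.** Those on the date of Visit 6 fall inside the double-blind period. Those in Weeks 12 to 14 fall in Period 2 and in the Week 0 to 24 Treatment Period tables. No section specifies a summary over Weeks 0 to 14.

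**The case against.** The strongest reply is that nothing is lost. Treatment-emergent events run to Week 24, events of special interest are tabulated by arm over the whole Treatment Period, and placebo has its own column. Reactions during the fourth infusion or later that day are inside the double-blind period. This stands. A reader might infer that the placebo-controlled comparison omits the fourth infusion, or a quarter of the safety data. The documents do not support that: the 25% is a dose count, the time affected is 14.3%, and the later events are reported, though mixed with other treatment.

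A reader might also infer that LY3462817 participants stopped at Week 14 are missing from the exposure tables. They are not. They are in the Period 1 duration table, and their fourth dose is in total dose, which SAP 4.6.1 sums over all infusions without a period limit. What is missing is about two weeks of duration per person.

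The boundary is also the protocol's own. Section 4.1 labels Period 1 as Visits 2 to 6, and section 4.2 describes the placebo-controlled period as lasting 12 weeks. Visit 6 appears in both periods, so the Week 12 infusion could be read as the first dose of Period 2. No text states the blind for that infusion specifically; it is inferred from the general blinding statement in the synopsis and the timing of the switch. These points limit the criticism of the SAP but do not supply a Weeks 0 to 14 summary.

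Finally, a window closing at Visit 7 gives the fourth infusion a nominal 14 days of follow-up against 28 for the others. That is a limit of the design, and still more than the dosing day alone.

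**Conclusion.** The concern holds as a gap in the planned summaries. The SAP places Weeks 12 to 14 in Period 2 although, under the protocol supplied, every arm is still on its randomised treatment. No planned safety or exposure summary therefore gives the whole randomised comparison. The size is 14 of 98 controlled days (14.3%), or 3.07 person-years overall and 0.77 on placebo, at nominal visit days and full retention. Duration after Week 12 is unreported for placebo and, on the natural reading of SAP 4.6.1, for LY3462817 participants stopped at Week 14.

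The likely source is a version mismatch. The SAP says it rests on the protocol dated 05AUG2020, and its section 1.2 has all subjects receiving LY3462817 in Period 2, a design under which closing the controlled period at Visit 6 would be coherent. The protocol supplied describes decisions of September 2020 and a different Period 2. This is an inference, since SAP 4.6.1 already speaks of subjects who remain on LY3462817.

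The primary analysis and its power are unaffected, because the Week 12 efficacy assessments are made before dosing.

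**What to change.** 1. Reconcile SAP 1.2 (Period 2 description), 4.1 (Treatment Period, period boundaries, post-baseline and follow-up baseline), 4.6.1 (exposure) and 4.6.2 (treatment-emergent window) with Protocol 1.3, 4.1 and 6.5.3.
2. If the protocol's present design stands, define in the SAP a placebo-controlled safety and exposure window from first infusion through Visit 7, or through the early discontinuation visit or the start of standard of care if earlier.
3. Over that window, summarise treatment-emergent events, events of special interest, laboratory tests, vital signs and exposure duration by arm for all participants. Keep the Week 0 to 24 tables as a second view.
4. Leave the Week 12 efficacy endpoint and the Period 1 and Period 2 labels unchanged. The concomitant-therapy rules (Protocol 6.5.1) and the interim and database-lock triggers (Protocol 9.5, SAP 4.8) depend on period or double-blind completion, so relabelling would reach further than this point needs.

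The cost is SAP wording and some extra programming. Visit 7 already collects adverse events, vital signs, hematology and chemistry, so no visits, samples or participants are added.
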